Supporting analyses for the secondary outcome of frailty will assess the outcomes of persistent major mobility disability (PMMD) and SPPB. PMMD is considered present when an individual fails to complete two successive 400-m walks (Newman, 2006; Pahor, 2014). The 400-m walk is a proxy for the ability to move without assistance from place to place within a community context, which is a key contributor to maintenance of independence in the community as one ages. Performance on the 400-m walk, a marker of major mobility disability, has been associated with morbidity, disability, hospitalization, and mortality (Pahor, 2014; Newman, 2003; Newman, 2006; Vestergaard, 2009) and was assessed in Look AHEAD-C. Those who failed the 400-m walk for the first time at their last scheduled clinic visit (and who are not adjudicated as

persistent failures), will be invited to return 6 months later for a repeat assessment to establish persistence.

The SPPB was developed to measure lower-extremity physical function as reflected in balance, gait speed, strength and endurance. It is comprised of the ability to stand with feet together in the side-by-side, semi-tandem, and tandem positions; time to walk 4-meters; and time to rise from a chair and return to the seated position 5 times (Guralnik, 1994). The SPPB was modestly expanded to minimize ceiling effects (which may occur when the original version is used for younger, more-well functioning cohorts). In this expansion, the holding time of the standing balance is increased to 30 seconds and a single leg stand is added (Simonsick, 2001). Additional supporting analyses are based on self-reported falls; Falls Efficacy Scale International (Yardley, 2005); and Pepper Assessment Tool for Disability (Rejeski, 1995), which includes 19 items, covering 3 domains: basic activities of daily living (ADL), mobility, and instrumental ADLs.

End-stage renal disease (ESRD) is the principal microvascular outcome and will be defined as renal replacement therapy (RRT) or death from nephropathy, and will be obtained by self-report through the six month telephone contact and biennial clinic exams, and by adjudication of death certificates.

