Frailty is the primary outcome for this aim and is a new aim because it has not been measured prior to LA-E. It will be assessed using the Fried criteria [Fried, 2001] developed during the Cardiovascular Health Study. Frailty classification is based on the presence of five frailty characteristics: 1) walking speed standardized based on median height and sex, 2) grip strength standardized based on body mass index (BMI) and sex, 3) energy expenditure standardized based on sex, 4) exhaustion based on self-report, and 5) weight loss of 10 lbs or more in the last year without trying or intending to (based on self-report). Walking speed will be assessed using the timed short walk included in the Short Physical Performance Battery (SPPB) and grip strength. Energy expenditure will be based on kcal/week of energy derived from the Paffenbarger physical activity questionnaire. Exhaustion will be assessed using the question from the Geriatric Depression Scale, "Do you feel full of energy?." Weight loss will be assessed by self-report. (We acknowledge that this is a difficult item to interpret for the LA cohort, and will also examine the impact on a construct without this item.) Based on these assessments, frailty will be classified into three stages: non-frail (no frailty characteristics present), pre-frail (1 or 2 frailty characteristics present), and frail (3 or more frailty characteristics present). Our primary analysis will classify a person as having prevalent frailty if they are classified as frail during either of the LA-E visits. The proportion of participants experiencing any frailty will be compared between randomized groups using logistic regression, with clinic site, sex, and time from randomization to classification of frailty or the last non-frail classification as covariates. Odds ratios and 95% confidence intervals will be used to summarize the relative effect of the intervention on frailty.

Supporting analyses: include persistent major mobility disability (PMMD) based on repeated assessments of the adjudicated 400-m walk, sensitivity analyses for frailty and PMMD, falls, fractures, SPPB, grip strength, and Pepper Assessment Tool for Disability (PAT-D).

PMMD is considered present when an individual fails to complete two successive 400-m walks [Newman, 2006; Pahor, 2014]. Death after an initial MMD determination will also be considered

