PMMD. Additionally, information used in the adjudication of MMD (i.e. self- or proxy report of inability to walk across a small room without the assistance of another person) in the absence of 400-m walk data will be collected every 6-months via telephone and will be used to ascertain PMMD. We will define PMMD based on the sequence of 400-m walks from LA-C (one) and LA-E (twice). In addition, those who failed the 400-m walk for the first time at their last scheduled LA-E clinic visit and who are not adjudicated as persistent failures will return 6 months later for a repeat assessment to establish persistence. The proportion of participants experiencing any PMMD will be compared using logistic regression models. The basic model will include an indicator variable for intervention assignment, follow-up time with covariate adjustment for sex and clinical site. Follow-up time for PMMD will be considered as the time until the initial MMD failure or last successful completion of the 400-m walk for those without PMMD. Odds ratios and 95%CI will be used to summarize the relative effect of the intervention on PMMD.

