Several **sensitivity analyses** will be performed for both frailty and PMMD: 1) covariates found to be predictive of missing outcomes will be entered into the logistic regression models to explore the effect of covariate dependent missingness on inference; 2) for the PMMD analysis, cases adjudicated as probable or possible MMD will be included as MMD cases to determine how robust the conclusions about the effect of the intervention on PMMD are to this broader classification of mobility disability, 3) for frailty, analyses will also be performed to compare the proportions not frail versus pre-frail or frail in each group, 4) multi-state survival models (PMMD) or transitional models for categorical outcomes will be used to compare the probability of transitions into and out of outcome states between participants randomized to the two intervention groups. Two absorbing states will be death and loss to follow-up. We will specifically evaluate the effect of the intervention on recovery from MMD or frailty. Recovery is defined as restoring the ability to complete a 400-m walk test after experiencing a MMD outcome or no longer being classified as frail. This evaluation will be accomplished by applying multi-state survival models to the disability and survival state data using the R msm and ELECT packages [van den Hout, 2013; Jackson, 2011] or using Proc Genmod of SAS™ to fit transitional models.

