Power: If 3800 participants are enrolled in LA-E and 8% in the DSE group will be classified as frail during LA-E, we project 80% power to detect an odds ratio of 0.70 (two-sided 0.05 type 1 error). Note that our preliminary data with a somewhat limited definition of frailty provide support for these assumptions: observed OR=0.75 [95% CI 0.57, 0.98] and 6.4% prevalence in the DSE group.

As noted earlier, LA-E plans to follow 3,800 participants through 2020, with collection of MMD data on two occasions, 2 years apart. If we assume 12.7% of the DSE group experience PMMD, a two-sided 0.05 probability of Type I error, and 1900 active participants in each group are followed for MMD, LA-E will have approximately 80% power to detect a 25% reduction in the

odds of PMMD in the ILI group compared to the DSE group. This percent relative reduction is consistent with what was observed in the LIFE [Pahor, 2014] trial (physical activity vs successful aging interventions) where the physical activity group had a 28% reduction in the hazard rate for PMMD.

5.4 Specific Aim 4 (secondary) is to test the hypothesis: the time until first occurrence of end stage renal disease (RRT or death from nephropathy) post-randomization will differ between intervention groups.

The primary outcome for diabetic nephropathy will be the first occurrence of **end stage renal disease (ESRD)**, defined as renal replacement therapy (RRT) or death from nephropathy. Information on outpatient and inpatient dialysis has been a crucial part of data collection since the beginning of the LA trial and has been collected every 6 months throughout. Renal transplants have been captured throughout follow-up, as well. This will continue in LA-E. The distribution of time to first occurrence of ESRD will be compared between ILI and DSE using survival analyses as described for total mortality (Section 5.1). Because data on ESRD will continue to be collected every six months in LA-E (as it was in LA and LA-C), censoring and follow-up times will cluster around these six month time points even though we will use the dates of the participant encounter to calculate follow-up time. Because 6-month intervals are fairly short and regular in length throughout follow-up, we will follow the commonly accepted recommendations [Leung, 1997] and will not complicate the analysis by considering interval censoring. All data since randomization will be used for analysis.

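### The SAP's death rule for persistent major mobility disability has no exception for a 400-m walk completed before death, so a participant who recovered and later died is scored as persistently disabled

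*Combined protocol and SAP*

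**What the plan says.** Protocol 1.4.2 and SAP 5.3 share the base definition: "PMMD is considered present when an individual fails to complete two successive 400-m walks". SAP 5.3 then adds the following.

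- **Death rule.** "Death after an initial MMD determination will also be considered" PMMD. No time limit or exception is attached. Protocol 1.4.2 does not mention death.
- **Data used.** "We will define PMMD based on the sequence of 400-m walks from LA-C (one) and LA-E (twice"). A first failure at the last LA-E visit, if not already adjudicated as persistent, is re-tested six months later.
- **Evidence without a walk.** Self- or proxy report of being unable to cross a small room unaided, "in the absence of 400-m walk data will be collected every 6-months via telephone and will be used to ascertain PMMD". An MMD determination is therefore wider than a failed walk.
- **Follow-up time covariate.** "Follow-up time for PMMD will be considered as the time until the initial MMD failure or last successful completion of the 400-m walk", the latter for those without PMMD.
- **Recovery.** In the sensitivity analyses, "Recovery is defined as restoring the ability to complete a 400-m walk test after experiencing a MMD outcome".
- **Death as its own state.** In the fourth sensitivity analysis (multi-state or transitional models), "Two absorbing states will be death and loss to follow-up".

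The main PMMD comparison is a logistic regression on any PMMD. Its power statement assumes 12.7% PMMD in DSE, 1,900 participants per arm, a 25% reduction in odds and a two-sided 0.05 test, for about 80% power.

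**The concern.** What makes the outcome persistent is that the first failure is confirmed. Counting a death that occurs before confirmation was possible is defensible. Counting a death after the participant has completed the walk is not, because persistence was tested and not found.

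As written, the rule covers both situations. It therefore adds all-cause death after recovery to an outcome that will be read as evidence on mobility, in a trial where all-cause mortality is itself a co-primary outcome. It can also override the study's own confirmation step: a participant who fails for the first time at the last visit, passes the six-month repeat and then dies within follow-up is still a case. For such cases the follow-up covariate stops at the initial failure, so the later completed walks are ignored there too.

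**Working it through.** **1. Classify the possible sequences under the SAP text.** There are up to three walks, and the LA-E walks come "with collection of MMD data on two occasions, 2 years apart", so a completed walk can fall between a failure and a death.

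| LA-C walk | Exam 1 | Exam 2 | Then | Two successive failures? | Death rule applies? | Scored |
|---|---|---|---|---|---|---|
| fail | fail | – | any | yes | – | PMMD |
| fail | dies before it | – | – | no | yes | PMMD |
| fail | missed | dies before it | – | no | yes | PMMD |
| fail | pass | pass | alive | no | no | not PMMD |
| fail | pass | – | dies | no | yes | **PMMD** |
| fail | pass | pass | dies | no | yes | **PMMD** |
| pass | pass | fail, then passes 6-month repeat | dies | no | yes | **PMMD** |

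In the last three rows the participant has recovered by the SAP's own definition. Rows four and six differ only in the death, yet the PMMD score differs.

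**2. Reproduce the stated power.**
- DSE odds: 0.127/0.873 = 0.1455. Times 0.75 gives 0.1091, so the ILI proportion is 0.1091/1.1091 = 0.0984.
- Pooled-variance formula: z = [(p1 − p2)√n − 1.96√(2p̄q̄)] / √(p1q1 + p2q2), where p̄ is the mean of the two proportions and q = 1 − p.
- z = [0.02863 × 43.59 − 1.96 × 0.4472] / 0.4467 = 0.83, so power is 79.7%. The stated figure of about 80% reproduces.
- Expected DSE cases: 0.127 × 1,900 = 241.

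**3. Size of the recovered-then-died group, by assumption only.** The documents do not give the inputs. Assume MMD in 10–30% of an arm, recovery in 10–40% of those, and later death in 5–20% of the recovered.
- Low: 0.10 × 0.10 × 0.05 = 0.05% of an arm, about 1 of 1,900, or 0.4% of the 12.7%.
- High: 0.30 × 0.40 × 0.20 = 2.4%, about 46 of 1,900, or 19% of the 12.7%.

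**4. Effect on the odds ratio.** Let x be the recovered-then-died share of each arm. Suppose the 12.7% in DSE includes x, and the odds ratio among the remaining cases is 0.75.

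| x in DSE | x in ILI | Observed odds ratio | Power |
|---|---|---|---|
| 0.05% | 0.05% | 0.751 | 79% |
| 2.4% | 2.4% | 0.792 | 63% |
| 1.2% | 0.6% | 0.720 | – |
| 0.6% | 1.2% | 0.811 | – |

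Example, third row:
- DSE without x: 0.127 − 0.012 = 0.115, odds 0.1299; times 0.75 gives 0.0975, a proportion of 0.0888 in ILI.
- Adding 0.006 gives 0.0948, odds 0.1047.
- Observed odds ratio: 0.1047/0.1455 = 0.720.

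Fourth row, by the same steps: DSE without x is 0.121, ILI is 0.0936 + 0.012 = 0.1056 with odds 0.1180, and 0.1180/0.1455 = 0.811.

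The two unequal rows only show that the shift can go either way. They are not forecasts.

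**5. Look for a planned analysis that would reveal this.** Sensitivity analysis 4 separates death and models recovery, but in a different model. No listed analysis repeats the logistic comparison with the death component removed or restricted.

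**The case against.** **The authors may have meant death to stand in for the second, confirming failure.** The sentence follows directly on the two-walk definition, so this is plausible. No passage says it, however, and an analyst who programs the sentence as written will score the recovered participants as cases.

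**The trigger is an adjudicated determination, not just one failed walk.** This is correct. Cases adjudicated only as probable or possible enter in one sensitivity analysis. It affects who is exposed to the rule but does not remove the recovered.

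**Death is already handled separately.** This is partly so. Sensitivity analysis 4 treats death as absorbing and examines recovery, but it leaves the logistic odds ratio untested.

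**The assumed sizes are generous.** This stands. Recovery from an LA-C failure can first be seen at Exam 1, and LA-E runs from February 2016 to July 2020, so there are at most about four and a half years in which to die afterwards. SAP 5.1 projects 509 DSE deaths over the whole trial, about 20% of half of the 5,145 randomized (509/2,572.5). An upper value of 20% death after recovery thus equals whole-trial mortality in a much shorter window. People with MMD may die faster, but the documents give no figure.

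**Two stronger readings are tempting, and the documents support neither.**
- A reader might infer from the excess of about 40 DSE deaths in SAP 4.2 that the rule inflates the PMMD benefit of ILI. That is a running count for the trial. LA-C began in August 2013, and a death before its walk cannot follow an MMD determination from that walk. The count says little about deaths after recovery.
- A reader might infer that protocol and SAP contradict each other. The protocol is silent on death, leaves analysis detail to the SAP (1.5), and itself refers to adjudicated persistence. The gap needs aligning, but it is not a contradiction.

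**Conclusion.** Wrong as written, and minor. The literal rule scores as persistently disabled a participant who recovered under the SAP's own definition and later died, while the same participant alive without two successive failures is not a case. That follows from the wording and needs no assumption.

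The consequence for the estimate cannot be determined from the documents. Equal numbers of such deaths would dilute the odds ratio; unequal numbers could enlarge or shrink the apparent effect. The range of 1 to 46 per 1,900, and the odds ratios derived from it, rest wholly on assumed MMD, recovery and death rates and on the 12.7% including these cases, which the SAP does not state. A claim that the rule favours ILI, or counts the mortality difference twice, would describe only one of the possible scenarios.

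PMMD supports a secondary aim. Both co-primary outcomes and the main frailty analysis are unaffected, and the stated PMMD power is not in error.

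**What to change.** 1. In SAP 5.3, replace the death sentence with: *Death after an initial MMD determination is counted as PMMD only if no 400-m walk was completed between that determination and death.*
2. Do not add a condition that death must precede the next scheduled walk. Someone who fails in LA-C, is too disabled to attend Exam 1 and dies before Exam 2 would then not qualify through the death rule, and could be lost unless the six-monthly telephone reports identified them. The no-completed-walk condition keeps such people as cases and removes only the recovered.
3. Put the same rule in protocol 1.4.2.
4. Add one sensitivity analysis: the PMMD logistic model without the death component.

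The cost is one sentence in each document and one extra model run on data already being collected. The downside is slightly fewer PMMD events.

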While retention during LA and LA-C has been balanced between intervention groups, missing data is always a concern for analyses. They are inevitable and statistical methods must take this into account in order to draw valid conclusions. Information collected during the study related to reasons that values are missing will be helpful in examining assumptions about missing data, e.g., whether data are missing completely at random, missing at random, or non-ignorably missing. In general, our analytical plans follow the recommendations of the 2010 National Academy of Sciences report regarding the treatment of missing data in clinical trials [National Research Council, 2010]. To identify factors that provide information as to the probability of missing outcomes, we will first compare the baseline characteristics of participants who do and do not have specific follow-up measures. Sensitivity analyses to determine how conclusions from primary outcome models may be affected by missing data initially will be performed by including covariates predictive of missing observations in such models. Such sensitivity analyses are intended as a conservative reexamination of data to explore whether reasonable assumptions placed on missing data might alter an observed finding, but primary consideration will be given to the original analysis of the aim.

The linear mixed effects model fitted by maximum likelihood estimation is unbiased if missing data are unrelated to outcomes, i.e., if the data are considered missing at random or missing completely at random. Nevertheless, because it is not always known whether missing data are ignorable and because missing observations have the potential to alter the results of analyses, the pattern of missing data and dropouts will be examined between the two treatment arms. We will also examine whether the outcome is related to missingness by using logistic regression models to determine if the outcome measure at the follow-up times preceding the missed visit predicts that the next value is missing and if baseline values predict monotone missing outcomes (i.e. non-intermittent). If there are no systematic differences between those with and without missing data, the data will be considered to be observed (and missed) at random.

When missing outcomes are dependent on unobserved outcomes, potentially biased estimates of intervention effects due to differential missingness may occur. If this situation is suspected,

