then for continuous outcomes a multiple imputation approach will be developed that uses various underlying distributional assumptions for the missing observations within the imputation procedure to evaluate if overall conclusions from analyses change based on reasonable assumptions for the underlying distribution of the missing outcomes. Alternatively, selection models, or shared parameter random effects models, will be fit, and sensitivity analyses will be performed to check the robustness of study conclusions. For survival analyses, there will be right censoring of follow-up time; however, some individuals drop out without having complete follow-up. For these analyses, inverse probability weighting will be used to perform sensitivity analyses of the primary results relative to assumptions about those that dropped out.

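### The covariate-entry missing-data check for frailty and PMMD mixes a change in the odds ratio's meaning with any missing-data effect, and does not limit the added predictors to baseline

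*Combined protocol and SAP*

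**What the plan says.** The primary frailty analysis (SAP 5.3) is "logistic regression, with clinic site, sex, and time from randomization to classification of frailty or the last non-frail classification as covariates". For PMMD the basic model has "an indicator variable for intervention assignment, follow-up time with covariate adjustment for sex and clinical site". The effect measure is the odds ratio: "Odds ratios and 95% confidence intervals will be used to summarize the relative effect of the intervention on frailty".

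The first sensitivity analysis in 5.3, for both outcomes, is that "covariates found to be predictive of missing outcomes will be entered into the logistic regression models to explore the effect of covariate dependent missingness". It follows the general rule in SAP 4.4, where the initial sensitivity analyses "will be performed by including covariates predictive of missing observations in such models". Just before that rule, 4.4 says that baseline characteristics of participants with and without follow-up measures will be compared. A later paragraph of 4.4 adds a logistic screen for whether earlier outcomes predict missingness: "if the outcome measure at the follow-up times preceding the missed visit predicts that the next value is missing".

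For other outcome types 4.4 goes further. It names multiple imputation for continuous outcomes when missingness is suspected to depend on unobserved values, with selection or shared-parameter models as an alternative. For survival outcomes, "inverse probability weighting will be used to perform sensitivity analyses of the primary results relative to assumptions about those that dropped out". Neither weighting nor imputation is named for the binary frailty and PMMD outcomes. Item 4 of the 5.3 sensitivity analyses adds multi-state or transitional models with death and loss to follow-up as absorbing states. SAP 4.4 keeps the main weight on the original analysis.

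**The concern.** A sensitivity analysis for missing data is read by putting two estimates side by side: if they agree, the result is called robust. That reading requires both to estimate the same quantity. Odds ratios are not collapsible. Adding a covariate that predicts the outcome moves the odds ratio away from 1 even with complete data and perfect balance between arms. The primary model conditions on only a few variables, and the check conditions on more, so a gap between them need not come from missing data. Equally, a small real bias in the same direction as the shift could leave no gap.

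The second issue is which covariates may enter. Item 1 in 5.3 does not say baseline. If a predictor measured after randomization and changed by ILI were entered, such as physical function at LA-C, part of the intervention effect would be adjusted away. At stake is the robustness statement for a secondary aim, not the primary estimate.

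**Working it through.** **Inputs from the SAP.** Section 5.3: "If 3800 participants are enrolled in LA-E and 8% in the DSE group will be classified as frail during LA-E", odds ratio 0.70; for PMMD, 12.7% in DSE, odds ratio 0.75, 1900 per group; two-sided 0.05. Section 4.3: loss of 2% per year, and clinic measures on more than 95% of active participants. Over 4.5 years that is 9% lost; with at most 5% missed among the rest, up to 1 − 0.91 × 0.95 = 13.6% missing.

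**Assumptions (not in the documents).** The added covariates form one normal score Z whose effect has SD s = 0.5, 1 or 1.5 on the log-odds scale (AUC about 0.64, 0.75, 0.83). The planned odds ratio is taken as the primary-model value, and Z as what is added to that model. Missingness is 15% per arm.

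**Step 1. The plan's own power.**
- Frailty, ILI rate: 0.08/0.92 × 0.70 = 0.0609 odds, or 5.74%. With 1900 per arm a two-proportion calculation gives power of about 79%.
- PMMD, ILI rate: 0.127/0.873 × 0.75 = 0.1091 odds, or 9.84%. Power is about 80%.

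Both agree with the stated 80%. The standard error of the frailty log odds ratio is √{[1/(0.08 × 0.92) + 1/(0.0574 × 0.9426)]/1900} = 0.130. For PMMD it is 0.103.

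**Step 2. Shift with nothing missing.** In each arm, solve for the intercept α in p = ∫ expit(α + sz) φ(z) dz. The adjusted odds ratio is exp(α_ILI − α_DSE). Frailty at s = 1: α_DSE = −2.832 and α_ILI = −3.217, so the adjusted odds ratio is exp(−0.384) = 0.681.

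| s | Frailty, 0.700 becomes | Shift in SE | PMMD, 0.750 becomes | Shift in SE |
|---|---|---|---|---|
| 0.5 | 0.696 | 0.05 | 0.744 | 0.07 |
| 1 | 0.681 | 0.21 | 0.727 | 0.31 |
| 1.5 | 0.655 | 0.52 | 0.699 | 0.69 |

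If the true odds ratio is 1, the adjusted value is 1.000 at every s.

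**Step 3. Adding missingness that depends on Z (s = 1, frailty).** Missing probability is expit(γ + δz), with γ set to give 15%. The complete-case rate in each arm is ∫(1 − m)p / ∫(1 − m). The adjusted complete-case odds ratio equals the adjusted full-data one, 0.681, in every row.

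| Missingness | Rates among observed, DSE and ILI | Complete-case odds ratio | Adjusted |
|---|---|---|---|
| δ = 0.7 in both arms | 7.22%, 5.15% | 0.697 | 0.681 |
| δ = 1 in DSE only | 6.91%, 5.74% | 0.820 | 0.681 |
| δ = 1 in ILI only | 8.00%, 4.91% | 0.594 | 0.681 |

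Row 1: missing data moved the odds ratio by 0.4% (0.700 to 0.697), but the reader sees a 2.4% change (0.697 to 0.681), most of it the change of quantity. Masking is the converse: a bias taking the complete-case value from 0.700 to about 0.681 would show no change on adjustment. Rows 2 and 3: biases of 17% and 15% are clearly exposed.

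**Step 4. Weighting with the outcome model unchanged.** In simulation (3800 participants, 600 runs, s = 1), full-data against weighted odds ratios were 0.698 and 0.696 (both arms), 0.702 and 0.702 (DSE only), and 0.697 and 0.694 (ILI only). Weighting returned the full-data value within 0.003 each time.

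**Step 5. If a post-randomization predictor were entered, nothing missing.** If half of the conditional log odds ratio runs through Z, the adjusted value is the square root of the step 2 value: for frailty √0.696 to √0.655, or 0.83 to 0.81; for PMMD √0.744 to √0.699, or 0.86 to 0.84. The share of one half is an assumption, and these figures follow almost directly from it.

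**The case against.** The strongest reply is that the check does what 5.3 says it is for. If missingness depends on the entered covariates and arm, the adjusted complete-case model is valid for the conditional odds ratio, and its test of no effect is valid. With a true odds ratio of 1 and missingness tied to the score in DSE only, the complete-case odds ratio was 1.17 with 22% simulated rejection, while the adjusted one was 1.00 with 4%. A reader might infer from non-collapsibility that the check cannot show any effect of missing data, or that it always flatters ILI. Neither is supported: step 3 shows large arm-differential bias exposed, and the shift is away from 1 in whichever direction the effect lies, so it cannot make an effect out of none. This part of the reply stands.

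It is also fair that the shift is small beside the sampling error, that covariate strength is assumed, that retention has been balanced between arms, and that 4.4 gives priority to the original analysis. All of that limits the consequence.

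On post-randomization covariates, a reader might infer that the SAP plans to enter earlier outcomes into the logistic model. It does not say so. The rule in 4.4 follows a comparison of baseline characteristics; the screen on earlier outcomes sits in a separate paragraph that begins with linear mixed models and diagnoses the missingness mechanism; and 5.3 says frailty was not measured before LA-E. What stands is narrower: neither the rule in 4.4 nor item 1 in 5.3 restricts entry to baseline, and LA-C physical function measures exist.

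The reply leaves the comparison itself unrepaired. The models in item 4 do not re-estimate the primary odds ratio, and no weighting or imputation is named for these two outcomes.

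**Conclusion.** The point holds as a limited defect of one sensitivity analysis for a secondary aim. The contrast between the primary and the covariate-added odds ratio confounds a change of estimand with the missing-data effect. Under the assumed covariate strengths the change of estimand is about 1% to 6% for frailty and 1% to 7% for PMMD, or roughly 0.05 to 0.7 standard errors. That is enough to create or mask a small difference, but not to hide a large arm-differential bias. The direction away from 1 needs only prognostic predictors and a true odds ratio other than 1; the size rests on the assumed score SD and missingness pattern.

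Entry of post-randomization predictors is an open reading of the text rather than a stated plan. It could matter more if taken, since the loss would be whatever share of the effect those predictors carry.

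**What to change.** In SAP 5.3 sensitivity analysis 1, and in 4.4 as it applies to binary outcomes:

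- Leave the primary outcome model exactly as specified and refit it with inverse-probability-of-observation weights, the method 4.4 already plans for survival outcomes, or after multiple imputation.
- Put the predictors of missingness, including any earlier outcomes, only in the weight or imputation model. Let their effects differ by arm, since the large biases in the working arise when they do.
- Compare this odds ratio with the primary one; both then target the same quantity.
- If covariate entry is kept as well, limit it to baseline covariates, and state that its odds ratio is conditional on more variables and is expected to differ somewhat from the primary one with complete data.

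The cost is SAP wording, a little more programming and slightly wider intervals. Weighting or imputation of this kind, like covariate entry, does not address missingness that depends on unobserved frailty or mobility.
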